`Medication Washout: If patients are eligible to participate in the study, and they are taking psychiatric medications at the time of recruitment, they will have the psychiatric medications tapered off. The patients will be off of all medications for three weeks before PET scanning. This medication-free treatment period is necessary to obtain imaging and clinical outcome data that are not significantly influenced by previous medications. The design will also allow us to measure the clinical response to lurasidone that is independent from an interaction with the previous medications. Patients will meet with a psychiatrist from MIND or DES at least weekly

in person during this time. A CGI, HAM-D, YMRS, psychotic symptoms of BPRS and CSSRS will be performed at least weekly to detect new onset of manic symptoms or clinical deterioration. Only patients who still meet inclusion criterion of HAM-D>15, including atypical depression items addendum, at the clinical appointment one week before the scheduled PET scan will continue.

Patients who no longer meet inclusion criteria at the end of the period, including those that are no longer sufficiently depressed, will not continue with imaging and will be offered up to 6 months of open label outpatient treatment.

Frequency of Clinical Visits: Throughout the study, outpatients will meet with a treating MIND or DES psychiatrist at least once a week in-person. Subjects will do the washout on the 4 Center or 5 South unit if clinically warranted. Inpatients will be evaluated by their physician at least three times weekly. In addition, all inpatients are monitored at intervals on an around-the-clock basis by ward clinical staff. During the washout period, inpatients will generally see a psychiatrist daily, except for weekends and holidays.

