Clinical Treatment: Open-label lurasidone will be taken by participants after a meal, beginning at 20 mg daily for the first two weeks. At that time, the dose can be increased to 40 mg daily for two weeks. Dosage will be raised only if the participant is tolerating the medication and has not been rated "much improved" or "very much improved" on the CGI improvement scale for that week. At week 4, blood samples will be drawn to measure blood glucose and lipids for safety monitoring. Treatment will be up to 4 weeks or until the second PET scan. Study visits will be weekly with a MIND or DES psychiatrist, unless the participant is rated much improved at week four, in which case visits will be biweekly thereafter. Additional visits can be scheduled at the study doctor's discretion for purposes of clinical management. At each visit, the study psychiatrist will complete the MADRS, YMRS, CGI, CSSRS, psychotic symptoms of BPRS, and SAFETEE-GI. Patients will complete self-rating forms at each visit. Participants with a Clinical Global Improvement (CGI) score of 6 ("much worse") or 7 ("very much worse") on two consecutive weeks during the trial will be terminated early from the study. Patients without alcohol or benzodiazepine use disorder may receive benzodiazepines for insomnia or anxiety/agitation (maximum dose equivalent to 4 mg of lorazepam per day). All patients may also receive zolpidem or diphenhydramine for insomnia or agitation.

Lurasidone and all laboratory tests will be provided for free of charge to the participant. Participants will receive six months of free outpatient treatment including the treatment obtained through this protocol, with treatment visits at least monthly.

Emergency Procedures: A research psychiatrist will be available by cell phone at all times during the study. Patients requiring urgent admission at the time of a study visit will be brought to the CUMC Emergency Department by the study physician and if necessary, security assistance will be provided. The treating psychiatrist will arrange non-urgent hospital admissions, preferably to the NYSPI 5-South unit. If patients refuse hospitalization but the clinical team determines that this is needed, the team will arrange all necessary interventions including contacting the local crisis team, family or Emergency Medical Services.

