Patients lost to follow-up: Upon enrollment, patients will be asked to provide the name and phone number of at least two persons who will likely know their future whereabouts. These people will be contacted if the subject is lost to follow up.

Criteria for Early Discontinuation

1) Intolerable side effects of lurasidone

2) Refusal to continue regimen and willingness to receive open treatment 3) DSM-IV criteria for a manic episode or score > 12 on the YMRS

4) During the washout period, if subjects score a six (much worse) or seven (very much worse) on the CGI- I, the protocol will be discontinued. If the participants do not tolerate the washout because of marked agitation, severe anorexia such as inability to drink adequate amount of fluids, or suicidal ideation or behavior with plan or intent, the protocol will be discontinued. In these cases, subjects will be offered open clinical treatment.

5) During the lurasidone treatment phase, if subjects score a six (much worse) or seven (very much worse) on the CGI-I for two consecutive weeks, the trial will be terminated early. If there is clinical reason to change to open treatment, such as onset of psychotic symptoms, manic symptoms of clinical concern, active suicidal ideation on two consecutive visits, the clinical team will evaluate whether the risks outweigh the benefits of continuing protocol.

6) If the patient requests withdrawal for any reason.

7) The PI judges that it is medically unwise to continue in the study, for example if the subjects are unable to comply with the study procedures and rules.

Radiotracer Information

Name of the radiolabeled drug/compound: [18F]DOPA

Manufacturer and other information: [18F]DOPA will be synthesized by the David Gardner PET Center at CUMC. IND 140398 is to use [18F]DOPA with lurasidone (latuda) as per this PSF. Lurasidone (Latuda) will not be used in an off label manner, however.

IND is approved IND# 140398. IND is held by PI/CU Investigator [name], MD

Data Analysis Plan

The aim of the analyses is to provide feasibility data for a larger grant application. We will visualize all data to assess for trends that are not detectable in standard statistical analyses due to the small power of this preliminary study.

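### No SAFETEE-GI rating is specified before the first lurasidone dose, so pre-existing complaints may be mistaken for drug side effects

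*Combined protocol and SAP*

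**What the plan says.** All references are to the combined protocol and SAP.

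- **Medication Washout** sets the pre-drug battery: "A CGI, HAM-D, YMRS, psychotic symptoms of BPRS and CSSRS will be performed at least weekly". No side-effect scale is in it.
- **Clinical Treatment** sets the on-drug battery, due at each visit: "the study psychiatrist will complete the MADRS, YMRS, CGI, CSSRS, psychotic symptoms of BPRS, and SAFETEE-GI". It adds self-rating forms, which are not named.
- The taper applies to some patients only. If "they are taking psychiatric medications at the time of recruitment, they will have the psychiatric medications tapered off". The section then states: "The patients will be off of all medications for three weeks before PET scanning".
- Inclusion criterion 5 nevertheless permits benzodiazepines and hypnotics for the whole study.
- Treatment is uncontrolled: "Open-label lurasidone will be taken by participants after a meal". No comparison group is described.
- Two rules call for a judgement about tolerability. For the dose step, "Dosage will be raised only if the participant is tolerating the medication" (the same sentence adds a condition on improvement). The first item under Criteria for Early Discontinuation is "Intolerable side effects of lurasidone".
- The **Data Analysis Plan** aims at preliminary data to support a larger funding application, says all data will be plotted, and acknowledges low power. It defines no side-effect endpoint, no treatment-emergent rule and no way of attributing a complaint to the drug.

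**The concern.** A side-effect rating taken only on drug mixes two things: what the patient already had and what began after the first dose. Patients who reach lurasidone are, by the entry rule, still depressed (HAM-D above 15 at the appointment one week before the scan). Some will be taking a benzodiazepine or hypnotic, and some will recently have been tapered off other medication. Each of these can plausibly produce complaints that a clinician would also consider as possible drug effects.

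In a randomised trial, the control arm would show the background level of complaints. Here only the patient's own earlier rating could do so, and the plan does not call for one. A baseline that was not collected cannot be recovered at analysis. What is at stake is modest: whether the SAFETEE-GI data can be read as change since starting the drug when the larger study is planned, and whether the clinician judging tolerability has a like-for-like earlier rating to look back on.

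**Working it through.** The plan gives no side-effect rate, sample size or power figure, so there is nothing to reproduce. The check compares the schedules.

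**Step 1. The two batteries side by side.**

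| Instrument | Washout | Lurasidone phase |
|---|---|---|
| CGI | yes | yes |
| YMRS | yes | yes |
| BPRS psychotic items | yes | yes |
| CSSRS | yes | yes |
| HAM-D | yes | not listed |
| MADRS | not listed | yes |
| SAFETEE-GI | not listed | yes |

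SAFETEE-GI is thus in neither part of the schedule before drug. The depression scale also changes from HAM-D to MADRS, so HAM-D items recorded in washout have no listed on-drug counterpart.

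**Step 2. Is a pre-dose rating specified elsewhere?** Recruitment Procedures refers to clinical assessments and medical screening under IRB#4815, but names no side-effect scale. PET Imaging requires a physician safety check within 48 hours of a scan. CSSRS is the only instrument named for it, and its timing relative to the first dose is not given. No section states a SAFETEE-GI rating before lurasidone.

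**Step 3. Is there an attribution rule?** None was found in any section.

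**Step 4. Who is affected?** Depression applies to every patient who continues. Benzodiazepine or hypnotic use applies to those who take them. The taper applies only to patients medicated at recruitment.

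**Step 5. Can the effect be sized?** Let *p* be the share of patients with a complaint before the first dose, *r* the share with a truly new one (independent of the first), and *k* the fraction of pre-dose complaints that persist, are recorded on drug and are put down to lurasidone. The apparent rate is then 1 − (1 − *kp*)(1 − *r*). None of *p*, *r* or *k* is in the documents. The values below are assumptions, used only to show the spread.

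| *r* | *k* = 0 | *k* = 1, *p* = 0.30 | *k* = 1, *p* = 0.60 |
|---|---|---|---|
| 0.20 | 0.20 | 1 − 0.70 × 0.80 = 0.44 | 1 − 0.40 × 0.80 = 0.68 |
| 0.40 | 0.40 | 1 − 0.70 × 0.60 = 0.58 | 1 − 0.40 × 0.60 = 0.76 |

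The result runs from no inflation (*k* = 0) to a large one (*k* = 1), according to inputs that the documents do not supply. The direction is clear: if on-drug complaints are counted without a baseline, any *kp* above zero raises the count. The size is unknown.

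**The case against.** The strongest reply is that nothing in the plan depends on this rating. This is a small imaging pilot with no planned side-effect rate, and tolerability is not named as a feasibility measure. Neither the dose-step condition nor the first discontinuation criterion cites a SAFETEE-GI score. Both are left to psychiatrists from services that see outpatients at least weekly throughout the study, with HAM-D and CGI during washout, so complaints before drug do not go unobserved. The three weeks off medication is meant to limit carry-over. The washout stopping rules remove patients who become much worse or cannot tolerate the period, so the most severe taper reactions should not reach lurasidone. The documents also do not describe the content of SAFETEE-GI or say whether it records onset or suspected cause.

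Most of this stands, and it limits the point. It does not close the gap. HAM-D and CGI measure illness severity, not side effects, and give no like-for-like comparison with a first on-drug SAFETEE-GI. The stopping rules catch severe cases, not the milder complaints that persist. Since the plan says all data will be plotted, SAFETEE-GI will be shown in some form, and as scheduled the plot would start on drug.

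It could also be said that the instruction to rate at each visit includes a pre-dose visit, or that IRB#4815 supplies a baseline. Neither is stated. The instruction sits inside the description of lurasidone treatment, and a rating made at IRB#4815 screening would come before any taper.

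**Conclusion.** The point holds in a limited form. No pre-dose SAFETEE-GI and no attribution rule are specified and no comparator is described, so some pre-existing complaints may be mistaken for lurasidone side effects. The size cannot be estimated from the documents, and weekly clinical contact partly mitigates the problem. It is a minor weakness in supporting data. It does not touch the PET comparison or any sample-size or power figure.

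A reader might infer more, and the documents do not support it:

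- *That a planned side-effect rate is biased upward.* No such rate is defined.
- *That on-drug entries will be read as lurasidone effects.* No section says so; clinicians may well discount complaints they saw in washout.
- *That the dose step and early stopping are distorted.* Neither rule uses the instrument, so any influence would come through clinical judgement and is only possible.
- *That complaints are first noticed on drug.* That is true of the SAFETEE-GI form, not of clinical observation.
- *That inflation reaches 44–76%.* Those figures need assumed rates and also require every pre-dose complaint to persist, be recorded and be attributed to the drug.

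The verdict assumes that no pre-dose SAFETEE-GI is set out in IRB#4815 or in study forms that were not supplied.

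**What to change.** Two short additions would settle it.

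1. In Research Procedures: the study psychiatrist completes SAFETEE-GI once for every participant at the last existing visit before the first lurasidone dose, including participants who need no taper.
2. In the Data Analysis Plan: on-drug SAFETEE-GI is displayed per patient as change from that rating, and a complaint counts as treatment-emergent only if it is new or worse than at that rating. Where the pre-dose rating is missing, show the raw on-drug rating and mark it as not classifiable.

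If a pre-dose rating is already intended, a sentence saying when it is done is enough, provided it falls after any taper.

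The cost is a few extra minutes at a visit already scheduled, with the same instrument and rater and no added staff. The change does not make the data controlled: a complaint that starts after the first dose could still come from the illness. It does remove the part that was demonstrably there beforehand. No dose, stopping rule or other clinical rule changes.

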Research Protocol: 18F-DOPA PET to Elucidate the Antidepressant Mechanism of Lurasidone in Bipolar Disorder

9/17/2019

Recruitment Procedures

Patients will be recruited through referrals from treating outpatient psychiatrists, or from clinics at Columbia University. Advertisements will be placed through the Columbia University website including the "RecruitMe" site and on advertising sites such as Craig's List. A website that describes the study will be created. Messages will be posted on email list-serves of mental health clinicians describing the study and asking for referrals. Subjects will be recruited by Depression Evaluation Service members through IRB#6669R.

Study staff and investigators will contact subjects who respond to advertising efforts to screen and recruit eligible individuals. For clinical patients at Columbia, only subjects who the clinical staff has identified as appropriate will be approached. The clinical staff will first ask the patient if he or she can be approached by research staff. Only if the subject agrees to be approached will the staff from this study do so. All potential subjects will be given the telephone number of the research coordinators who will discuss the purpose and procedures of the research and screen the subjects for potential eligibility.

Texts of written materials to be distributed via advertisements and websites will be submitted to the IRB for approval before they are distributed.

1. Initial screening will be completed as detailed in IRB#6879R or IRB#6669R.

2. If eligible, subjects will be asked to sign the consent form for IRB# 4815 ([name]). Participants will then be given a physical exam, laboratory test (via blood draw) and psychiatric examinations as performed under IRB#4815. IRB#4815 allows for clinical assessments, a medical screening for significant illness, a screening for drugs of abuse, a developmental history and acquisition of blood samples for genetic analyses. IRB#4815 allows for the above procedures so that subjects can enter any of several different types of studies and protocols.

3. If eligible for IRB#4815, subjects will be given a detailed verbal explanation of this study by a research psychiatrist. During the consent process, the consenting psychiatrist will obtain a history of participants' past radiation exposure. Participants will then give written informed consent if they choose to participate in the study.

Inclusion Criteria

Criterion	Method of Assessment

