1)Ability to provide informed consent	Clinical interview
2) Diagnosis of bipolar I disorder, bipolar 2 disorder or	DSM-IV by means of SCID
bipolar disorder NOS and currently meeting criteria for a	
major depressive episode	
3) Depression of sufficient severity to score at least 16 on the	Hamilton Depression Rating
first 17 items of the Hamilton Depression Rating Scale	Scale
including the atypical depression items addendum	
4) Age 18-50 years old	Clinical interview

5) Patients who were on psychiatric medication at	Clinical interview
presentation will have failed that regimen, as defined as not	
achieving at least partial remission after an adequate dose of	
medication for at least six weeks. Benzodiazepines and	
hypnotics are allowed throughout the study	
6) Females of child-bearing potential must be willing to use	Clinical interview
an acceptable method of birth control throughout the study:	
abstinence, birth control pill, male condom, IUD, depo-	
provera, Norplant, male sterilization or female sterlization	
7) Subject is likely to tolerate medication washout if	Clinical interview
indicated	
8) Must be enrolled in IRB#4815	Review of records

Exclusion criteria

Criterion	Method of Assessment
1)Diagnosis of any other major psychiatric disorders such as	As defined by DSM-IV by
schizoaffective disorder, current psychotic depression, or	means of SCID; urine drug
current drug or alcohol abuse (within two months before the	screen
study) or recent drug or alcohol dependence (within six	
months before the study); anorexia nervosa or bulimia	
nervosa within in the last year; Meet DSM-IV criteria for	
manic episode at the time of screening	
2)Previous failed trial of lurasidone, defined by at leastv six	Clinical interview
weeks of treatment at the dose of 20 mg per day or more.	
Experienced intolerable side effects of lurasidone in the past.	
Taking any medications that are contraindicated with	
lurasidone unless there is a plan to stop these as part of the	
washout.	
3)History of clinical deterioration when any of the	Clinical interview
medications that the patient is taking at presentation have	
been discontinued in the past if they will be discontinued as	
part of the washout.	
4)First-degree family history of schizophrenia if the subject	Clinical interview
is less than 33 years old.	
5)Significant active physical illness, including blood	Medical history by a
dyscrasias, lymphomas, hypersplenism, endocrinopathies,	physician, physical exam,

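### Entry sets no YMRS limit, yet a YMRS above 12 is a stopping rule, so a patient who already meets that rule may begin the medication taper

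*Combined protocol and SAP*

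**What the plan says.** **Stopping.** Under Criteria for Early Discontinuation, item 3 is "DSM-IV criteria for a manic episode or score > 12 on the YMRS". Item 4 is restricted to washout and item 5 to lurasidone treatment. Item 3 carries no such restriction.

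**Entry.** Exclusion 1 rules out a patient who meets criteria for a "manic episode at the time of screening". No other inclusion or exclusion item deals with current manic symptoms, and none mentions the YMRS. Screening and baseline work are delegated to other protocols, including "psychiatric examinations as performed under IRB#4815", whose content is not given.

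**Washout.** For eligible patients on psychiatric drugs, Medication Washout says "they will have the psychiatric medications tapered off", and then "The patients will be off of all medications for three weeks before PET scanning". The YMRS is first named here, in a set of ratings "performed at least weekly to detect new onset of manic symptoms or clinical deterioration". The section gives no YMRS value to act on and does not say whether the first rating comes before the first dose reduction.

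**Depression, for comparison.** Inclusion 3 reads "Depression of sufficient severity to score at least 16 on the" first 17 HAM-D items with the atypical addendum. The check one week before the scan is "Only patients who still meet inclusion criterion of HAM-D>15, including atypical depression items addendum".

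**The concern.** Item 3 has two limbs. The manic-episode limb has a counterpart at entry; the YMRS limb has none. Staff who follow the listed criteria can therefore withdraw medication from someone the protocol itself says should be stopped. If the score stays above 12, that patient leaves before any scan or lurasidone. The patient bears the risk of the taper and the study gains nothing from it.

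The washout ratings are also meant to pick up manic symptoms that are new. That needs a value from before the taper, and this protocol names none.

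A patient who needs no taper carries no taper risk, but a related gap exists. Medication Washout does not say whether its ratings apply to such a patient. If they do not, the first YMRS named is at the treatment visits under Clinical Treatment. Those come after a first scan with radiotracer and, normally, an arterial line.

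**Working it through.** The plan states no figure to reproduce on this point. The check compares the criteria and then works out the timing.

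**1. Entry against continuation**

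| Domain | Limit at entry | Limit for continuing or stopping | Matched? |
|---|---|---|---|
| Depression | HAM-D at least 16 (inclusion 3) | HAM-D above 15 one week before the scan (Medication Washout) | Yes: the same limit for whole-number scores |
| Manic episode | Excluded at screening (exclusion 1) | Stop (item 3, first limb) | Yes |
| YMRS score | None | Stop above 12 (item 3, second limb) | No |

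**2. Who falls in the gap**

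The patient is in a current depressive episode, has a HAM-D of at least 16, does not meet criteria for a manic episode, and scores 13 or more on the YMRS. No inclusion item (1 to 8) or exclusion item (1 to 16) is breached on account of that score. Item 3 is met from the outset, because it is not tied to a phase.

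**3. How long the gap can last for a tapered patient**

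Call the first dose reduction day 0. Assume that the at-least-weekly ratings are counted from that day.

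- First required YMRS: day 0 (rated on the day the taper starts) to about day 7.
- Earliest scan: taper length T plus three drug-free weeks = T + 3 × 7 = T + 21 days, with T of 0 or more, so day 21 or later.
- From the first required rating to the earliest scan: at least 21 − 7 = 14 days.

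So the exposure is 0 to about 7 days of taper, against 0 days if a qualifying YMRS is required first. The 14 days also show that weekly ratings should identify a tapered patient well before any tracer is given. For tapered patients the cost is the dose reduction already made.

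**4. How many patients**

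This cannot be computed. The document gives no sample size, no YMRS distribution and no proportion on medication at recruitment.

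**The case against.** The strongest reply is that the harm needs a patient with a YMRS of 13 or more to reach the first dose reduction unrated, or rated and ignored. Screening is done under other protocols, enrolment in one of them is inclusion 8, and any of them may include a YMRS. If one does, item 3 read as applying in every phase would already stop the patient, and only a cross-reference is missing.

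The group is also well filtered. Inclusion 5 requires that the current regimen has failed, and inclusion 7 that the patient is likely to tolerate washout. Exclusion 3 removes those who deteriorated when a drug now to be withdrawn was stopped before. There are weekly in-person visits, inpatient washout where warranted, and item 7 lets the PI stop a patient.

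Finally, the HAM-D parallel is imperfect. The pre-scan HAM-D check re-tests an inclusion criterion and so has to match it. A stopping rule aimed at emergent symptoms need not appear at entry.

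Much of this stands: the exposure is short, the group is probably narrow, and an unseen screening YMRS could close the gap in practice. None of it, however, supplies a YMRS limit at entry or requires a YMRS before the first dose reduction. The reading that item 3 covers only emergent symptoms is not in its text, which says nothing of onset or worsening. If that is the intention, it too needs a line.

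The no-taper case is conditional. Weekly visits apply to outpatients throughout, and the pre-scan HAM-D check is not confined to tapered patients, so a YMRS may well be done. The text does not settle it.

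**Conclusion.** The concern holds. The entry criteria and item 3 do not agree on the YMRS, and a patient scoring 13 or more can be eligible and stoppable at the same time. For a tapered patient the size is 0 to about 7 days of dose reduction before the first required rating. The upper end rests on counting the weekly ratings from the start of the taper. It also takes item 3 at its word as applying in every phase, and takes it that no screening YMRS is obtained and acted on; this protocol requires neither.

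The frequency is unknown and may be low. This is a patient-safety correction that should be made because it is cheap. It is not a flaw that undermines the study. Confidence is medium, because the screening protocols cannot be seen.

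**What to change.** Make two linked changes:

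- Add YMRS above 12 to exclusion 1, so that it matches both limbs of item 3.
- Require one YMRS of 12 or below, at or after screening and before the first dose reduction. Where there is no taper, require it before the first PET scan. A recent rating from the screening protocols counts, so nothing is repeated where one exists.

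The cost is one line in exclusion 1 and at most one extra rating per patient, on a scale the study already uses. The downside is that a few patients whose score might have settled to 12 or below will be screened out or will need a second rating.

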PET Imaging: Each subject will undergo two PET scans with [18F]DOPA at the David A. Gardner PET Center at [name]. One scan will be before lurasidone is initiated and the second will be four weeks (+/- one week) after starting lurasidone. Patients will not eat within 12 hours of the PET scan with the exception of a low-protein meal more than four hours before the scan. A urine pregnancy test will be done on females on the day of each PET scan, before the scan, to assure that pregnancy has not occurred between the time of laboratory tests at screening, during which a serum pregnancy test is conducted, and the PET scan. Patients will be given 150 mg of carbidopa PO within 120 minutes of the radiotracer injection. Carbidopa is used to prevent AAAD decarboxylation of the radiotracer so that it is bioavailable to cross into the brain. The subject will have an intravenous line placed for radiotracer injection. An arterial line will be placed in the radial artery of the other arm by an experienced physician, [name]. [name] will be present during the scan until the arterial line is removed. An MD clinician from the MIND Division will be on the CUMC campus and avilable during the scan via telephone. If [name] is not available, [name] or [name] will be present during the scan until the arterial line removed. Patients will have vital signs measured before radiotracer injection and after PET scan is complete. If there is an complication with the arterial line placement, including patient refusal at the time of scan, the scan will proceed without blood sampling.

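### The stated aim is feasibility data, but the only method the plan states is looking at plots; it commits in advance to no estimate, interval or feasibility count

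*Combined protocol and SAP*

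**What the plan says.** The Data Analysis Plan states its purpose first: "The aim of the analyses is to provide feasibility data for a larger grant application". It then states its method: "We will visualize all data to assess for trends that are not detectable in standard statistical analyses due to the small power" of what it calls a preliminary study. Nothing follows, and the section shows no sign of redaction.

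Other sections describe steps that would generate feasibility data, but none is made an outcome:

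- PET Imaging, on the paired design: "One scan will be before lurasidone is initiated and the second will be four weeks (+/- one week) after starting lurasidone". If the arterial line fails, "including patient refusal at the time of scan, the scan will proceed without blood sampling".
- Medication Washout, on patients who arrive on treatment: "they are taking psychiatric medications at the time of recruitment, they will have the psychiatric medications tapered off". Only those still above the depression threshold "at the clinical appointment one week before the scheduled PET scan will continue". Patients who no longer qualify at the end of the period, "including those that are no longer sufficiently depressed, will not continue with imaging".
- Clinical Treatment, on ratings: "At each visit, the study psychiatrist will complete the MADRS, YMRS, CGI, CSSRS, psychotic symptoms of BPRS, and SAFETEE-GI".

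**The concern.** Aim and method do not meet. Feasibility data for a grant are quantities: how variable the paired PET change is, and what share of patients get through washout, stay eligible, complete both scans and have arterial data. A plot can display such data, but it does not estimate them or show how uncertain they are.

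The reason given for plotting is also weak. Low power means the data hold little information relative to their noise. A pattern that a standard analysis cannot separate from noise is not separated from it by being looked at.

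At stake is what the larger study is built on. If the PET outcome, the quantification method and the denominators are settled after the data are seen, the planning figures may depend on those choices without showing it. A secondary risk is that an open search with no named outcome picks out chance patterns.

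**Working it through.** **Step 1: what the plan commits to.** The documents contain no figure to reproduce. They give no sample size, effect size, SD, error rate or progression criterion, and describe power only as small. They also name no PET outcome parameter, quantification method, primary clinical measure, estimator or interval.

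**Step 2: what the protocol will generate.** Each patient who completes has two scans, which gives a paired change and its SD. Washout, the eligibility check, the early-discontinuation rules and the provision for scanning without blood each give a count.

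**Step 3: two details an estimation plan must settle.**

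- *Arterial blood.* A scan may go ahead without it. If a patient has blood at one scan only and each scan is quantified by whatever method is available, the paired change includes the difference between methods.
- *Clinical scale.* Medication Washout lists the HAM-D among its weekly ratings. Clinical Treatment lists the MADRS and not the HAM-D. The same depression rating scale before treatment and at the second scan is therefore not assured. The CGI appears in both lists.

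**Step 4: precision, for assumed n = 10 and n = 20.** These sample sizes are assumptions. Normal data are assumed for the SD and the correlation.

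*SD of change.* The 95% CI is s × √[(n−1)/χ²(0.975)] to s × √[(n−1)/χ²(0.025)], with n−1 degrees of freedom.

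- n = 10: √(9/19.023) = 0.69 and √(9/2.700) = 1.83.
- n = 20: √(19/32.852) = 0.76 and √(19/8.907) = 1.46.

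*Derived sample size.* For a paired comparison, N is proportional to SD²/δ² for a fixed difference δ, so the multipliers are squared.

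- n = 10: 9/19.023 = 0.47 and 9/2.700 = 3.3.
- n = 20: 19/32.852 = 0.58 and 19/8.907 = 2.1.

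*Mean change.* The half-width of the 95% CI is t(0.975, n−1) × SD/√n.

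- n = 10: 2.262/√10 = 0.72 SD.
- n = 20: 2.093/√20 = 0.47 SD.

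*Completion.* Exact (Clopper-Pearson) 95% CI, assuming 80% complete.

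- 8 of 10: 44% to 97%.
- 16 of 20: 56% to 94%.

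*One pre-named plot with no true association.* The chance of |r| ≥ 0.5 is the two-sided tail of t = 0.5 × √[(n−2)/(1−0.25)] with n−2 degrees of freedom. The cutoff of 0.5 is also an assumption.

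- n = 10: t = 0.5 × √(8/0.75) = 1.633 on 8 df, probability 14%.
- n = 20: t = 0.5 × √(18/0.75) = 2.449 on 18 df, probability 2.5%.

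Looking at more plots raises these probabilities. By how much cannot be said, because the plan gives neither the number of plots nor how the measures correlate.

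**The case against.** The plan is candid. It calls the study preliminary and admits small power, and its second sentence can be read as saying that tests would be uninformative, so the data will be inspected descriptively. Mentioning standard analyses may imply that some will be run. Nothing bars the investigators from reporting an SD or completion counts, and the phrase feasibility data may be meant to cover them. The intervals will in any case be wide.

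Much of this stands, and it limits the point. A reader might infer that the plan intends to report trends picked by eye as drug effects; the text does not say so. A reader might infer that SDs and counts will not be reported; the text supports only that they are not committed to in advance. A reader might also infer that a spurious pattern is likely. The documents give no sample size, cutoff or number of plots, so that cannot be claimed. Several of the listed scales may also vary little here, since current psychotic depression is excluded and a YMRS score above 12 is a discontinuation criterion.

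What does not stand is the idea that a pilot needs no more than plots. Estimates with intervals require no hypothesis test and no extra patients. If standard analyses are intended, none is named. Wide intervals are no reason to leave them out, because the width is what whoever plans the next study needs to see.

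**Conclusion.** The concern holds in this form: the one method stated does not deliver the stated aim, and the plan commits in advance to no estimate, interval or feasibility count. That conclusion rests on the text alone and needs no assumed sample size.

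The size is illustrative. At 10 to 20 patients, the SD of change is known only to within 0.69 to 1.83 times the estimate at the lower number and 0.76 to 1.46 times at the higher. A sample size taken from the point estimate without its interval would hide that uncertainty. The chance-pattern risk is secondary, and its size is unknown beyond the single-plot figures.

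This should be fixed, but it does not undermine the study. It concerns what is committed to and reported; no visit, scan or treatment rule is affected.

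**What to change.** Replace the second sentence of the Data Analysis Plan with a short estimation plan:

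1. **PET outcome.** Name one outcome and one quantification method, applied the same way to both scans of a patient. State how scans without arterial blood are handled: either a blood-free method for all patients, or an arterial method where blood exists with a blood-free method as sensitivity analysis. Report the paired mean change and the SD of change, each with a 95% CI.
2. **PET-clinical association.** Name one, using a scale measured both before treatment and at the second scan. Reconcile the HAM-D and MADRS lists, or use a measure common to both. Report it with a 95% CI and label it exploratory.
3. **Feasibility counts, with exact 95% CIs:**
   - washout completed, among patients who begin the taper;
   - still eligible for the first scan, among all enrolled, with earlier washout exits counted as not continuing;
   - both scans completed, among patients with a first scan and among all enrolled;
   - arterial sampling obtained at both scans, counted per patient, among patients with both scans.
4. **Plots.** Keep them as descriptive and hypothesis-generating. Delete the wording that they show trends standard analyses cannot detect.

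The cost is a few sentences and simple computing on data the protocol already generates, apart from settling the clinical scale. The real demand is choosing the PET outcome and method before the data are seen. The intervals will be visibly wide, and the fix does not narrow them. The gain is honest uncertainty and planning figures committed to in advance.
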